HIGH FAT VS HIGH PROTEIN AND APPETITE HORMONES

NCT # 04518930

Document Date: 03/06/2024

Study protocol

Study design and participants

The study design utilized a parallel-arm intervention, employing a non-blind randomized clinical trial format with two distinct treatment groups. This study enrolled fifty-two healthy Jordanian women from a private nutrition clinic in Amman through randomization.

This study was conducted in accordance with the ethical guidelines outlined in the Declaration of Helsinki. The research procedures involving study participants received approval by the Institutional Research Board committee at the University of Jordan (No. 19/2021/180). Furthermore, the study was registered on ClinicalTrials.gov (No. NCT 04518930). Written informed consent was obtained from all individuals who participated in the study.

Inclusion and exclusion criteria

The study's inclusion criteria encompassed women aged between 30 and 40 years, with a body mass index (BMI) ranging from 25 to 35 kg/m². The included age group comprises predominantly overweight and obese individuals attending the nutrition clinic, demonstrating high adherence to the study protocol. These individuals engaged in light exercise 1-3 times per week (activity factor 1.375) and adhered to a routine of consuming three regular meals, along with two daily snacks. They maintained a water intake of eight cups and ensured a sleep duration of 8 hours. Additionally, participants were required to have no known allergies, particularly to nuts, especially peanuts and yogurt.

Conversely, women were ineligible for the study if they met any of the following conditions: age below 30 years or above 40 years, BMI below 25 kg/m² or above 35 kg/m², engaged in little or no exercise or engaged in moderate to heavy exercise, were pregnant or lactating mothers, had allergies to nuts, peanuts, yogurt, milk, or milk products, were

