using medications, hormonal therapy, supplements, oral contraceptives, or herbal/botanical products claimed to suppress appetite. Furthermore, exclusion criteria encompassed women with hormonal disturbances, including those in a menopausal state, and those within their menstrual cycle days or within one week prior, commonly experiencing hyperphagia due to elevated progesterone levels. Additionally, individuals with chronic diseases and metabolic disorders such as cardiovascular diseases, diabetes, hypertension, kidney diseases, thyroid disorders, gastrointestinal diseases, polycystic ovary syndrome, or androgen disorders were excluded, following a weight-reducing diet, experiencing sleep disorders, or sleeping less than 8 hours per day, and consuming less than 8 cups of water per day were also excluded from the study.

Sample size determination

The required sample size for the study was determined using the formula:

$n = 2 * (Z\alpha + Z\beta)^2 * SD^2 \div \delta^2$, where n represents the required number of participants in both the treatment and placebo groups. $Z\alpha$ and $Z\beta$ are the values from the standard normal distribution corresponding to specific confidence levels of 95% and a two-sided α of 0.05 ($Z\alpha = 1.96$) and a power of 80% ($Z\beta = 0.84$). SD refers to the standard deviation (pooled), while δ represents the estimated difference between the treatment and placebo groups.

Based on the above equation, the sample size calculation indicated that approximately 20 subjects were needed for each arm of the trial to detect a change of 1.76 μ U/mL in insulin levels between the treatment and placebo groups, with 80% power and 5% significance. The standard deviation

(SD) was assumed to be 2.1. Therefore, $n = 2 * (1.96 + 0.84)^2 * (2.1)^2 \div (1.76)^2 \approx 22$ participants per group.

To account for potential participant dropouts and to enhance the statistical power of the analysis, the number of participants was increased to 26 women per group.

Overview of the study design and procedures

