The study employed a two-arm parallel design, consisting of 52 participants who were randomized into two groups. The Greek yogurt group ($n = 26$) received one serving (380 g, 200 kcal) of zero-fat Greek yogurt, and the peanut group ($n = 26$) received one serving (35 g, 200 kcal) of unsalted peanuts. Due to one participant from each group dropping out and not attending the second visit, only 25 subjects were included in the study analysis in each group.

All participants attended two visits to the clinic. During the initial visit, participants were instructed to arrive fasting for 10-12 hours, during which anthropometry and body composition analysis were conducted. They also received education and instructions to follow a three-day low-calorie diet totaling 1200 kcal, comprising breakfast, snack 1, lunch, snack 2, and dinner, prior to the interventions. On the second visit (post-diet visit), participants received and consumed their snacks, completed the visual analog scale (VAS) questionnaire and blood samples were withdrawn.

Treatment/intervention and randomization

Intervention

Two distinct interventional snacks were provided to the participants: plain Greek yogurt and peanuts. In the Plain Greek yogurt group ($n=25$), each participant consumed 380g of plain Greek

yogurt, equating to approximately 200 calories. In the peanut group, (n=25) each participant consumed 35g of roasted, unsalted peanuts, providing approximately 200 calories.

The plain Greek yogurt (non-flavored /30g protein/13.5g carbohydrate/0g fat) was procured from the supermarket and stored in the refrigerator until serving. The peanuts (roasted, unsalted, with skin/ 8.4g protein/7.6g carbohydrate/17.5g fat) were purchased one day prior to the serving date to preserve their attributes. They were meticulously prepared in a safe and sterile manner, portioned into small transparent pouches, each containing 35g. These packed peanuts were then stored in a dry, room-temperature environment until the serving date. Table 1 shows the macro and micronutrients composition of the two interventional snacks.

The intervention was provided to each participant upon arrival at the clinic based on pre randomization and they were asked to consume it at 1:00 pm.

Randomization

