The participants were assigned to two groups sequentially, following a predetermined randomization list. "Peanut" and "Greek yogurt" were each written clearly in Arabic on 26 folded papers. The list was created by randomly selecting folded papers from a basket, each containing either the label "peanut," or "plain Greek yogurt". The groups were then identified as the peanut group and the Greek yogurt Group based on the random selection of each participant .

All participants adhered to a 1200 kcal diet plan, including breakfast, snack 1, lunch, snack 2, and dinner. This diet plan remained consistent for all participants over three consecutive days, except during the second visit, where specific snacks were provided based on the randomization list.

Data collection and assessment

Pre-diet visit

During the initial visit, participants were provided with a three-day low-calorie diet menu totaling 1200 kcal. This menu included breakfast, snack 1, lunch, snack 2, and dinner, along with a follow-up sheet. They were instructed to adhere to the foods listed in the diet menu and to refrain from consuming peanuts or any peanut-based products, as well as Greek yogurt, during snack 1 and snack 2. Additionally, they were briefed on the necessity of daily follow-up via phone to monitor their compliance with the given instructions. Body composition analysis was performed using bioelectrical impedance analysis (Inbody 770). To categorize participants into groups, they were randomly allocated based on a pre-determined randomization list.

Anthropometric and body composition analysis

Before the body composition analysis test, each participant visited the clinic after overnight fasting for a period of 10-12 hours. The analysis was conducted using bioelectrical impedance technology, which automatically recorded several parameters, including weight, height, BMI, skeletal muscle mass, soft lean mass, fat mass, and abdominal circumferences. To ensure precise readings, participants were advised to wear lightweight clothing and remove any metal items, such as accessories, belts, money, and socks before the test.

Post-diet visit

On the second visit, scheduled after three days of adhering to the 1200 Kcal diet, all participants arrived at the clinic at 1:00 pm. Prior to their arrival, they had breakfast at home at 9:00 am. Upon arrival, a trained healthcare professional collected baseline blood samples from each participant.

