At 1:00 pm, participants in the plain Greek yogurt and peanut groups consumed their assigned snacks. Following snack consumption, a validated VAS questionnaire was distributed to assess sensations and appetite levels at 0 minutes (1:00 pm), 30 minutes (1:30 pm), and 60 minutes (2:00

pm). Additionally, one hour after their arrival, at 2:00 pm, a second blood sample was collected from all participants. Throughout this period, participants were situated in a stress-free environment designed for relaxation and comfort, with soft music played to enhance their experience. No adverse events were reported by any of the participants following snack consumption.

Appetite perceptions

Appetite sensation was evaluated using a validated VAS questionnaire, designed to measure subjective ratings of hunger, fullness, satiety, prospective food consumption, and desire to eat. The VAS questionnaire included questions assessing “how strong is your feeling of” hunger, fullness, and desire to eat or “how much food can you eat right now” with anchors of “not (much) at all” to “extremely/an extreme amount”.

Participants were instructed to indicate their sensations on the scale at various time points during the study: upon arrival, 30 minutes, and 60 minutes after consuming the snack. This allowed us to discern the impact of consuming Greek yogurt and peanuts on appetite perceptions over time. The decision to assess at 30 and 60 minutes was based on the rapid increase in gut hormones following food intake, with their secretion peaking around 1-2 hours later. The VAS questionnaire was self-administered, ensuring a convenient and straightforward assessment for the participants.

Biochemical analysis

The collected blood samples (baseline and after 60 minutes of intervention) were labeled with a unique code to ensure proper identification before being transported to the medical laboratory.

The blood samples were drawn into plain tubes containing separation gel and left undisturbed until coagulation occurred. After coagulation, serum was separated from the blood cells through centrifugation at 882 $\times g$ for 20 minutes. The resulting serum was then carefully transferred into Eppendorf tubes and stored at -20 °C to preserve the integrity of the peptides for subsequent analysis. These storage procedures adhered to the recommendations outlined in studies conducted by Hallworth and Lobely.

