To determine differences between the means of normally distributed continuous variables in both the plain Greek yogurt and peanut groups, a Student t-test for independent samples was employed. Additionally, a paired sample t-test was used to assess variations in means of normally distributed variables before and after snack consumption in both groups. In instances where variables displayed significantly skewed distributions, medians were compared using the Mann-Whitney U test for independent samples, while paired samples were compared using the Wilcoxon Signed Rank test. A two-way repeated measures ANOVA was performed to test the main and interaction effects of Greek yogurt, peanuts, and time on appetite and insulin hormones. Additionally, the repeated measures procedure of the General Linear Model (GLM) was utilized to analyze the impact of plain Greek yogurt and peanuts on appetite perceptions over time. Correlations between gut hormones, insulin, and anthropometric measurements were assessed using the Pearson two-tailed bivariate test for continuous variables. All p-values are two-tailed, and a significance level of $p \leq 0.05$ was considered.

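### With a snack in both arms and no no-snack arm or session, the within-arm before–after tests and the time main effect cannot isolate a snack's effect; conclusions should rest on the yogurt-versus-peanut difference in change, which is planned but not given priority

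*Combined protocol and SAP*

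**What the plan says.** All references are to the combined protocol and SAP.

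- **Arms.** Study design and participants describes a parallel trial "employing a non-blind randomized clinical trial format with two distinct treatment groups". Under Intervention, "Two distinct interventional snacks were provided to the participants: plain Greek yogurt and peanuts", each portion providing about 200 kcal. No third arm is described.
- **Sessions.** Under Overview of the study design and procedures, "On the second visit (post-diet visit), participants received and consumed their snacks". The first visit covers body measurements and diet instruction, so no woman is observed without a snack.
- **Timing.** Post-diet visit gives arrival at 1:00 pm with a baseline blood sample, and says of the participants: "Prior to their arrival, they had breakfast at home at 9:00 am". It continues: "At 1:00 pm, participants in the plain Greek yogurt and peanut groups consumed their assigned snacks". The second blood sample is at 2:00 pm, appetite is rated on the VAS at 0, 30 and 60 minutes, and everyone rests with soft music during the hour.
- **Tests.** Statistical analysis plans independent-samples tests between arms (Student t or Mann-Whitney). It adds that "a paired sample t-test was used to assess variations in means of normally distributed variables before and after snack consumption in both groups", with the Wilcoxon signed rank test for skewed variables. It then plans a two-way repeated measures ANOVA with main and interaction effects for the hormones, and a repeated measures GLM for the VAS ratings. One two-sided 5% threshold applies to all of them.
- **Interpretation.** Appetite perceptions says of the repeated ratings: "This allowed us to discern the impact of consuming Greek yogurt and peanuts on appetite perceptions over time". Statistical analysis also uses the word impact for the VAS model.

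**The concern.** A before–after test answers whether a variable moved during the hour. It answers whether the snack moved it only if nothing else would have. Here every woman goes from four to five hours after breakfast and spends that hour resting in the clinic. Hunger ratings, ghrelin or insulin could change under those conditions with no snack at all, in either direction. An upward drift in hunger would hide a real reduction; a downward drift would look like one.

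Randomisation does not protect these tests, because the drift is present in both arms. What is at stake is the kind of statement the trial can support. The design supports how much yogurt differed from peanuts. It does not support that either snack, taken alone, raised or lowered a hormone or rating. The plan gives both kinds of test equal standing and does not say which one carries the conclusion.

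**Working it through.** **1. What each test estimates.** Let D be the mean 1:00-to-2:00 pm change that would occur with no snack; randomisation makes it the same in expectation in both arms. Let Sy and Sp be the mean additional changes due to yogurt and to peanuts. For a variable measured twice, with equal arms:

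| Planned test | Quantity tested | Free of D? |
|---|---|---|
| Paired test, yogurt arm | D + Sy | No |
| Paired test, peanut arm | D + Sp | No |
| Time main effect | D + (Sy + Sp)/2 | No |
| Arm-by-time interaction | (D + Sy) − (D + Sp) = Sy − Sp | Yes |
| Group main effect (mean of both times) | (Sy − Sp)/2 | Yes |

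The last row follows because the expected baseline difference between randomised arms is zero. D could be separated from Sy or Sp only with a no-snack arm or session, and there is none.

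**2. The plan's own figure.** Sample size determination gives 2 × (1.96 + 0.84)² × 2.1² ÷ 1.76² = 2 × 7.84 × 4.41 ÷ 3.0976 = 22.3, stated as 22 per group. That reproduces. It concerns a difference between two groups, so it offers no support for the before–after tests. At 25 analysed per arm, a difference of 1.76 ÷ 2.1 = 0.84 SD has about 83% power in a two-sided t-test.

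**3. Illustration of size, hormones only.** Inputs from the documents: 25 women analysed per arm, two blood samples, two-sided 5% level. Assumed: no effect of either snack, normally distributed changes with equal SD, and a common drift of d SDs of the change score. The documents give no value for d, so a range is shown.

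- Paired test: noncentral t with 25 − 1 = 24 df and noncentrality d√25.
- Time main effect: noncentral t with 50 − 2 = 48 df and noncentrality d√50.
- Arm-by-time test: the drift cancels, so noncentrality is 0.

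| d (assumed) | d√25 | Paired test significant | d√50 | Time effect significant | Arm-by-time significant |
|---|---|---|---|---|---|
| 0 | 0 | 5% | 0 | 5% | 5% |
| 0.2 | 1.0 | 16% | 1.41 | 28% | 5% |
| 0.3 | 1.5 | 30% | 2.12 | 55% | 5% |
| 0.4 | 2.0 | 48% | 2.83 | 79% | 5% |
| 0.5 | 2.5 | 67% | 3.54 | 93% | 5% |

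Simulation (40,000 trials each at d = 0, 0.3 and 0.5) gave about 5%, 30% and 67% for the paired test, and 4.9% to 5.0% for the between-arm test of change.

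These figures do not carry over to the VAS ratings, which have three time points. The algebra in step 1 does carry over, taken for each change from time 0.

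**The case against.** **The valid comparison is already planned.** This is correct and important. The independent-samples tests come first in the section, and the ANOVA includes the interaction. A reader might infer that the trial has no sound analysis, or that the group main effect is also at fault. Neither follows: both are randomised comparisons. What is missing is a statement that they, and not the before–after tests, carry the conclusions.

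**The paired tests are only descriptive.** The sentence on them makes no causal claim, the title of the document is comparative, and the documents report no conclusion about a single snack. The impact sentence under Appetite perceptions could also be read comparatively. This has some force, but the plan does not label the tests as descriptive, applies the same significance threshold to them, and uses the word impact for change over time in two sections.

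**The percentages are hypothetical.** This stands. They are power curves under an assumed drift and a snack that does nothing. A null effect of a 200 kcal snack is unlikely for insulin and gut hormones, and the protocol itself expects gut hormones to rise quickly after eating. For hormones that rise strongly the bias may be small. A reader should not take the figures as this trial's false-positive rate.

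**Two further inferences go too far.** One is that resting after the blood draw would lower the ratings. The text does not order the first rating relative to the draw, and it places that rating both at arrival and after the snack. The other draws on Sample size determination, where "n represents the required number of participants in both the treatment and placebo groups". No placebo group exists, but that is a separate sample-size matter and not evidence about the paired tests.

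**Conclusion.** The point holds, limited to the within-arm paired or Wilcoxon tests and the time main effect. That these tests mix snack effect with ordinary change follows from the design and does not depend on any assumed drift. The size of the resulting error is unknown: the documents give neither the amount nor the direction of ordinary change over the hour. It may be minor for strongly responding hormones, and is undetermined for ghrelin and the VAS ratings.

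No randomised estimate is biased by this, and the yogurt-versus-peanut comparison stands. The weakness is that the plan gives that comparison no priority and words change over time as the snacks' impact. It should be corrected, and analysis and wording changes are enough.

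**What to change.** 1. In Statistical analysis, name the yogurt-versus-peanut difference in change (the arm-by-time interaction) as the sole basis for conclusions about snack effects on hormones and VAS ratings. With two blood samples, this equals an independent-samples t-test on the change scores. For the VAS, report the between-arm differences in change at 30 and 60 minutes alongside the interaction test.
2. Keep within-arm changes as description: mean change with 95% CI, not offered as evidence of a snack effect. Treat the time main effect in the same way.
3. In Appetite perceptions and Statistical analysis, reword the impact statements to refer to yogurt relative to peanuts.
4. Add a sentence saying that, without a no-snack arm or session, the absolute effect of either snack cannot be estimated.

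The cost is some analysis text and a few sentences of interpretation; the data already collected are enough. The downside is that the trial gives up any claim that one snack on its own raised or lowered a hormone or rating.

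### The plan names no test as the yogurt-versus-peanut comparison of hormones and never adjusts for the pre-snack value; ANCOVA would settle both at almost no cost

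*Combined protocol and SAP*

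**What the plan says.** Each analysed woman has two values of every hormone. Under Post-diet visit, on arrival "a trained healthcare professional collected baseline blood samples from each participant", and at 2:00 pm, one hour later, "a second blood sample was collected from all participants". The overview of the design gives 25 analysed per arm.

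The Statistical analysis section lists these methods for the hormones:
- Between groups, "a Student t-test for independent samples was employed", with Mann-Whitney for skewed variables. The quantity compared is not stated: it could be the baseline, the 60-minute value or the change.
- Within groups, "a paired sample t-test was used to assess variations in means of normally distributed variables before and after snack consumption in both groups", with Wilcoxon for skewed variables.
- A two-way repeated measures ANOVA "to test the main and interaction effects of Greek yogurt, peanuts, and time on appetite and insulin hormones".
- Pearson correlations, with no time point given for the hormones.

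No covariate appears, and no test or model term is named as the one that compares the snacks. Yet Sample size determination is built on a between-group contrast: δ "represents the estimated difference between the treatment and placebo groups", and the target is a change of 1.76 μU/mL "in insulin levels between the treatment and placebo groups, with 80% power and 5% significance". That section does not say whether 1.76 and the SD of 2.1 refer to 60-minute values or to changes from baseline.

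**The concern.** The trial was sized for one between-arm difference, but the analysis section offers several results that might be taken for it. They do not have the same precision. The paired tests do not compare the arms at all. The ANOVA group main effect averages in a value taken before the snack, so under randomisation it estimates only half the 60-minute difference. The group-by-time interaction does compare the arms and does use the baseline, but through a simple subtraction, which is not in general the most efficient use.

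Two separate matters follow. The first is ambiguity, which naming any one between-arm test would cure. The second is efficiency: a pre-snack measurement has already been paid for, and covariate adjustment would use it better.

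**Working it through.** **Inputs.** From Sample size determination: difference 1.76, SD 2.1, two-sided α 0.05 (1.96), power 80% (0.84). From the design overview: 25 analysed per arm. Not in the documents, so assumed: r = 0.3, 0.5, 0.7 (correlation of pre-snack and 60-minute values) and k = 1, 0.7, 0.5 (pre-snack SD divided by 60-minute SD).

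**The plan's own figure.** n = 2 × (1.96 + 0.84)² × 2.1² ÷ 1.76² = 2 × 7.84 × 4.41 ÷ 3.0976 = 22.3, which reproduces the 22 per group. At 25 per arm an unadjusted t-test with SD 2.1 has 82.7% power (noncentral t, 48 df).

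**Variances.** Let S be the 60-minute SD. Per-woman variance of the quantity compared:
- t-test on the 60-minute value: S²
- group-by-time interaction (with two time points, identical to a t-test on change): S²(1 + k² − 2rk)
- ANCOVA: S²(1 − r²)

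The first exceeds ANCOVA by r²S². The second exceeds it by (1 + k² − 2rk) − (1 − r²) = (k − r)², times S². Neither excess can be negative, so ANCOVA is at least as efficient as both, apart from one degree of freedom and an average variance inflation of 1 + 1/46 = 1.022 for estimating the slope. By contrast, the interaction beats the 60-minute t-test only when r > k/2, which cannot be checked from the documents.

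**Power at 25 per arm, difference 1.76 (%).** ANCOVA uses 47 df and the 1.022 inflation. When 2.1 is read as the SD of the change, S = 2.1 ÷ √(1 + k² − 2rk).

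| k | r | 60-min t-test (2.1 = 60-min SD) | Interaction | ANCOVA | 60-min t-test (2.1 = change SD) | Interaction | ANCOVA |
|---|---|---|---|---|---|---|---|
| 1 | 0.3 | 82.7 | 68.9 | 85.3 | 93.0 | 82.7 | 94.5 |
| 1 | 0.5 | 82.7 | 82.7 | 91.2 | 82.7 | 82.7 | 91.2 |
| 1 | 0.7 | 82.7 | 96.3 | 98.0 | 61.4 | 82.7 | 87.6 |
| 0.7 | 0.3 | 82.7 | 80.1 | 85.3 | 85.2 | 82.7 | 87.6 |
| 0.7 | 0.5 | 82.7 | 90.4 | 91.2 | 73.3 | 82.7 | 83.8 |
| 0.7 | 0.7 | 82.7 | 98.2 | 98.0 | 54.5 | 82.7 | 81.9 |
| 0.5 | 0.3 | 82.7 | 84.6 | 85.3 | 80.8 | 82.7 | 83.5 |
| 0.5 | 0.5 | 82.7 | 91.8 | 91.2 | 71.0 | 82.7 | 81.9 |
| 0.5 | 0.7 | 82.7 | 97.5 | 98.0 | 57.7 | 82.7 | 84.6 |

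**Margins of ANCOVA, in points of power.**
- Against the better of the other two tests: −0.6 to +8.5 (60-minute SD), −0.8 to +8.5 (change SD).
- Against the worse: about +3 to +16 (60-minute SD), about +3 to +27 (change SD).
- Outside the grid, at r = 0 with 2.1 as the 60-minute SD, ANCOVA has 81.9% against 82.7% for the 60-minute t-test. Break-even is near |r| = 0.15.

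Simulation with a fitted ANCOVA agrees (about 85, 91 and 98% at r = 0.3, 0.5 and 0.7), with type I error about 5%.

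**Disagreement between tests, only if the t-test is on 60-minute values.** The t-test and interaction estimates then differ by exactly the chance pre-snack difference between arms. With 2.1 as the 60-minute SD, its standard error is k × 2.1 × √(2/25) = 0.59, 0.42 and 0.30 for k = 1, 0.7 and 0.5, or 34, 24 and 17% of 1.76. In simulation at the planned effect, exactly one of the two is significant in about 18 to 25% of trials at k = 1, 14 to 16% at k = 0.7 and 10 to 15% at k = 0.5.

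**The case against.** The strongest reply is that the ANOVA already uses the baseline and that its interaction is a valid snack comparison. That stands. Naming the interaction would remove the ambiguity, and ANCOVA is not needed for that purpose. What remains is efficiency, and against the better listed test the gain can be nil or a loss of under one point, as at k = r.

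A second reply is that r, k and the meaning of 2.1 are unknown. That also stands: no single gain can be quoted, only a range under stated assumptions. ANCOVA's advantage is that the choice does not depend on knowing them.

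Third, the text is in the past tense and 25 women per arm have been analysed, so pre-specification cannot now be restored. This limits the benefit but does not remove it.

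A reader might infer more than the documents support:
- That the baseline enters only as a time level and in the paired tests. This is not established, because the independent t-test and the correlations do not state their variable.
- That the plan contains two conflicting between-arm tests. If the t-test is on change, it is the same test as the interaction and they cannot disagree.
- That false-positive rates are inflated. Taking whichever result is significant would give about 7 to 9% per hormone for the 60-minute t-test and the interaction, and about 9 to 12% with the group main effect added. The plan does not say it will do this.
- That the arms will be compared through their paired tests. Paired power is 0.484 at n = 25 and a true standardised change of 0.4. If both arms had that same change, exactly one test would be significant in 2 × 0.484 × 0.516 = 50% of trials. This illustrates a misreading that the plan leaves open but does not state.

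**Conclusion.** The point holds as a free improvement. The plan neither adjusts for the pre-snack hormone value nor identifies its between-arm comparison. None of the listed methods is invalid, and the interaction is a sound comparison if it is the term that is read.

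If 2.1 is the 60-minute SD, power is about 85 to 98% for ANCOVA, 83% for the 60-minute t-test and 69 to 98% for the interaction. If 2.1 is the SD of the change, it is about 82 to 95% for ANCOVA, 55 to 93% for the 60-minute t-test and 83% for the interaction. So ANCOVA ranges from about 1 point worse to 8.5 points better than whichever listed test happens to be better, and protects against having chosen the worse one. These sizes rest on the assumed r and k. The absence of a covariate and of a designated comparison, and the ordering of the variances, do not.

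**What to change.** For each hormone, make the between-arm comparison an ANCOVA of the 60-minute value on snack group with the pre-snack value as covariate, both on the log scale if skewed. Report the adjusted yogurt-minus-peanut difference with its 95% CI.

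State what the independent t-test compares. Treat the paired tests as descriptive. If the ANOVA is kept, read the snack comparison only from the group-by-time interaction.

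If results are already known, label the ANCOVA post hoc and show it beside the planned analysis whatever it gives.

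For the VAS, use the 0-minute rating as a covariate only if it was taken before the snack. Post-diet visit has the questionnaire handed out after the snack, whereas Appetite perceptions has the first rating on arrival; these must be reconciled first.

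The cost is a few sentences, one degree of freedom and one SPSS re-run on data already collected. No new samples or participants are needed.

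### The planned snack main effect on hormones averages in the pre-snack sample, so it estimates half the 60-minute snack effect, and the plan does not say which term decides

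*Combined protocol and SAP*

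**What the plan says.** The design is parallel. The Overview of the study design and procedures states: "The study employed a two-arm parallel design, consisting of 52 participants who were randomized into two groups". One woman per arm dropped out, and "only 25 subjects were included in the study analysis in each group". Each woman therefore eats one snack only.

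Each woman gives two blood samples at the second visit. Under Post-diet visit: "Upon arrival, a trained healthcare professional collected baseline blood samples from each participant". Under Biochemical analysis, the two samples are named again: "The collected blood samples (baseline and after 60 minutes of intervention) were labeled with a unique code".

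For the hormones, the Statistical analysis section plans a two-way repeated measures ANOVA "to test the main and interaction effects of Greek yogurt, peanuts, and time on appetite and insulin hormones". It does not assign snack or time to the between-women or within-woman part of the model, and it names no term as the answer to the snack question. The same section also plans independent-samples tests between the groups (Student t, or Mann-Whitney for skewed variables), without saying which variables or time points they cover, and paired tests before versus after the snack. A repeated measures GLM is planned for the appetite ratings.

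**The concern.** Yogurt and peanuts are two levels of one randomised factor, so the model has one snack main effect, one time main effect and one snack-by-time interaction. The sentence lists the two snacks as if each had its own effect and gives all terms equal standing.

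The snack main effect is a poor measure of what the trial asks. It compares the arms on each woman's average of the two samples, and at the first sample nobody has eaten. Half of what it averages carries no snack effect, only noise. This is so even when the mixed model is specified correctly.

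What is at stake is interpretation. If the main effect is non-significant and another planned test is significant, the plan has no rule for which one is the result. If the main effect is given weight, a real difference of the size the trial was planned for would more often than not be missed at any correlation of 0.3 or above (SD 2.1 at each time).

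**Working it through.** **Inputs.** From Sample size determination: insulin difference 1.76 μU/mL, SD 2.1, two-sided 5%, power 80%. From the Overview: 25 analysed per arm. Not in the documents: the correlation r between a woman's pre-snack and 60-minute values, which is therefore varied. Also assumed: equal variances at the two times, and no expected arm difference before the snack (randomisation).

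**The plan's own figure.** n = 2 × (1.96 + 0.84)² × 2.1² ÷ 1.76² = 22.3 per arm, which reproduces the stated 22. With 25 per arm, the standard error of a 60-minute difference is 2.1 × √(2/25) = 0.594, so 1.76 ÷ 0.594 = 2.96. The noncentral t distribution with 48 df then gives 83% power.

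**What the main effect estimates.** (0 + 1.76) ÷ 2 = 0.88. This needs no value of SD or r.

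**Power if 2.1 is the SD at each time** (25 per arm):
- Snack main effect: difference 0.88, SD 2.1 × √((1 + r)/2).
- Snack-by-time: difference 1.76, SD of change 2.1 × √(2(1 − r)).
- 60-minute difference adjusted for the pre-snack value: difference 1.76, residual SD 2.1 × √(1 − r²).

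Example at r = 0.5: the main-effect SD is 2.1 × √0.75 = 1.819, its standard error is 1.819 × √(2/25) = 0.514, and 0.88 ÷ 0.514 = 1.71, which gives 39% power.

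| r | Snack main effect | Snack-by-time | 60 minutes, unadjusted | 60 minutes, adjusted |
|---|---|---|---|---|
| 0 | 54% | 54% | 83% | 83% |
| 0.3 | 44% | 69% | 83% | 86% |
| 0.5 | 39% | 83% | 83% | 92% |
| 0.7 | 35% | 96% | 83% | 98% |

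A simulation of 20,000 trials at r = 0.5 agrees: the main effect averaged 0.88 with 39% power, and snack-by-time averaged 1.76 with 83%.

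**Power if 2.1 is the SD of change.** The plan calls 2.1 only a pooled SD and speaks of detecting a change, so this reading is possible. The SD at each time is then 2.1 ÷ √(2(1 − r)). The SD of a woman's two-sample mean becomes 1.05 × √((1 + r)/(1 − r)), which is 1.43, 1.82 and 3.15 at r = 0.3, 0.5 and 0.8. Main-effect power is about 57%, 39% and 16%. Snack-by-time has 83% at every r. The halving to 0.88 is unchanged.

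**The case against.** The strongest reply is that the plan already contains sound tests. The same sentence plans the interaction, which targets the full 1.76, and the section also plans independent-samples tests. Nothing says the snack conclusion will come from the main effect. This stands: the halving affects one stated test, not the whole hormone analysis. What remains is that the plan tests that term and ranks nothing above it.

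Three stronger readings are tempting and are not supported.

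- A reader might infer that snack was entered as a repeated factor, with unrelated women paired. The text never says so. The name of the model is often used loosely for a group-by-time mixed model, and the section assigns independent-samples tests to the snack comparison and paired tests to before versus after. Only unstated factor roles are shown.
- A reader might infer that chance pre-snack imbalance makes a significant main effect untrustworthy. Under randomisation and no snack effect the test keeps its 5% error rate. Chance imbalance also reaches the unadjusted 60-minute comparison when r is above 0, and the change score when r is below 1.
- A reader might infer that snack-by-time alone is the cure. If 2.1 is the SD at each time, it has 54% power at r = 0, no better than the main effect, and 69% at r = 0.3. Both are below the 83% of a plain 60-minute comparison.

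**Conclusion.** The point holds in this limited form. The hormone ANOVA leaves the roles of snack and time unstated and names no deciding term, and one of the terms it tests estimates half the snack effect. The halving follows from the design alone: one sample before the snack, one after, and randomised arms.

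The loss of power depends on the assumed r and on the reading of the SD. For the planned insulin difference, main-effect power is about 54% to 35% over r = 0 to 0.7 if 2.1 applies at each time, against 83% for a 60-minute comparison. It is about 57% to 16% over r = 0.3 to 0.8 if 2.1 is the SD of change, against 83% for snack-by-time. The documents give insulin inputs only, so no size can be stated for the other hormones, although the halving applies to them too.

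This is more than missing detail, because it concerns how a planned test may be used. It does not invalidate the trial or its other planned comparisons.

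**What to change.** Replace the hormone ANOVA sentence with three statements:

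1. The model is a mixed ANOVA with snack (yogurt, peanut) as the between-women factor and time (pre-snack, 60 minutes) as the within-woman factor.
2. The yogurt-versus-peanut conclusion is not drawn from the snack main effect.
3. It is drawn from the 60-minute difference between arms adjusted for the pre-snack value, with snack-by-time reported as the matching ANOVA term.

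Apply the same rule to the appetite GLM if the 0-minute rating is taken before eating. The passages on that rating need reconciling first: Post-diet visit places the questionnaire after the snack, while Appetite perceptions places the first rating on arrival. If it does precede eating, and the snack effect is equal at 30 and 60 minutes, the main effect there targets two thirds of it: (0 + 1 + 1) ÷ 3.

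The cost is a change of wording and a re-run in the same software, with one covariate model per hormone. No new data are needed.
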